#### **10.9 Indicate the MHS information system(s) from which you will seek to obtain data**

If you do not know which system(s) contains the data elements you need, refer to the Guide for DoD Researchers on Using MHS Data or request guidance from an MHS data expert at: **[contact]**.

Below is a list of commonly used MHS systems. If the system from which you seek to obtain data is not listed below, list the name of the system in the "Other MHS Systems" category below

##### **PHI Systems:**

MHS Information System	Requesting Data
:AHLTA	:No
:CHCS	:No

##### **PII-Only Systems:**

MHS Information System	Requesting Data
No records have been added	

**De-Identified Data & Other Systems:**

Information System	Requesting Data
Other MHS System (May include PII and/or PHI) List other system here:	:  No
T Systems (to identify potential subjects during prescreening process)	

**10.10 Do you intend to merge or otherwise associate the requested data with data from any sources outside of the MHS, including other DoD systems that are not part of the MHS?**

- Yes, will merge data
- No, will not merge data

**10.11 Indicate the data elements about research participants or relatives, employers, or household members of the research participants that you will request from MHS hard copies or from MHS information systems.**

**If you will merge data, also indicate non-MHS data elements about research participants or relatives, employers, or household members of the research participants that you will have access to in any form or medium.**

Data Element(s)	MHS	Non-MHS Systems	MHS Hard Copies
1. Names			
2. Postal address with only town, city, state and zip code			
3. Postal address with all geographic subdivisions smaller than a state, including street address, city, county, precinct, zip code and their equivalent geocodes, except for the initial three digits of a zip code if, according to the current publicly available data from the Bureau of Census: 1) the geographic unit formed by combining all zip codes with the same three initial digits contains more than 20,000 people; and 2) the initial three digits of a zip code for all such geographic units containing 20,000 or fewer people is changed to 000			
4. Dates including all elements (except year)			

directly related to an individual, including birth date, admission date, discharge date, and date of death			
5. Ages over 89 and all elements of dates (including year) indicative of such age, unless you will only request a single category of "age 90 or older"			
6. Telephone numbers			
7. Fax numbers			
8. Electronic mail addresses			
9. Social Security numbers (SSNs)			
10. Medical record numbers			
11. Health plan beneficiary numbers			
12. Account numbers			
13. Certificate/license numbers			
14. Vehicle identifiers and serial numbers, including license plate numbers			
15. Device identifiers and serial numbers			
16. Web Universal Resource Locators (URLs)			
17. Internet Protocol (IP) address numbers			
18. Biometric identifiers, including finger and voice prints			
			

19. Full-face photographic images and any comparable images				
20. Any other unique identifying number, characteristic, or code (Diagnosis, DEERS ID, EDI-PI, Rank)				

If you are obtaining SSNs, provide a justification as to why and explain why a substitute cannot be used

**10.12 Do you believe it is possible for the MHS data to become identifiable because of triangulation, a small cell size, or any unique data element(s)?**

Triangulation means using different data elements that are not themselves identifiable but that when combined can be used to identify an individual. For example, triangulation would use rank and race together to determine the identity of an individual with a particular health condition.

Small cell size means that there is only a small number of eligible individuals that satisfy the category description. Guidance for acceptable cell size is available from the Centers for Medicare and Medicaid Services. For example, the rank category of four star generals with a particular diagnosis may be less than 30, so the rank category may need to be expanded to include lower ranks.

A unique data element includes any unique features that are not explicitly enumerated in the categories of data in rows 1 – 20 of the table above (in Section 10.10), but that could be used to identify an individual. Unique data elements include characteristics that are not themselves identifying, such as the rank of general or admiral, or a race or gender, but within the context of other information could be identifiable.

- Yes, I believe there is a reasonable possibility the MHS data will become identifiable
- No, I believe there is no reasonable possibility the MHS data will become identifiable

**10.13 Have you completed and uploaded an appropriate HIPAA document ( i.e. HIPAA Authorization will be obtained or Waiver/alteration of HIPAA Authorization is being requested)?**

- Yes
- No
- N/A

**10.14 Managing Data (Data Management and/or Sharing Plan) and/or Human Biological Specimens for this Study:**

Include in this section the plan for acquiring data (both electronic and hard copy), access during the study, data/specimen storage and length of time stored, shipment/transmission, and the plan for storage and final disposition at the conclusion of the study. Describe any data agreements in place for accessing data within and/or outside of your institution (e.g., Data Sharing Agreement, Data Use Agreement, Business Agreements, etc.)

As outlined in the procedures section, data acquired will initially be obtained by the investigator via T-system™ home screen during the pre-screening process. Data collection will occur from the time the subject provides informed consent through the conclusion of the data collection period. As the primary outcome, subjective pain level will be obtained upon administration of intramuscular ketorolac then 30 and 60 minutes after administration. As the secondary outcome, adverse effects will be assessed for at 30 and 60 minutes after administration of intramuscular ketorolac. Descriptive statistics will also be obtained on the Ketorolac Research Form after informed consent is obtained.

The subjective pain levels will be annotated on the three VAS forms. The descriptive data and adverse effects will be annotated on the WBAMC Ketorolac Research Form. These forms will be placed within the document envelopes for the duration of the study. At the end of each study day, the data from each

study subject will be transcribed on to the Excel document on the PIs government issued laptop. The laptop will physically be in the PIs possession for the duration of the study.

The only human biological specimen which will be obtained will be urine. It will be used for a POC UHCG test in order to assess for pregnancy. These specimens will be obtained, handled, processed, and destroyed in accordance with WBAMC ED and hospital policies. The results of the POC UHCG will be reported verbally to the attending and/or via the T-System comments section in EHR, which does not require access to the subject's individual EHR for their specific ED encounter.

The subject's EHR will not be accessed for any reason for the purposes of this research. All PHI or PII will be gathered on paper and will be provided voluntarily by the study subject. This information will be de-identified after consent is obtained and only the study subject randomized number will be used for identification.

All paper documents will be held in a locked locker in the WBAMC ED for the duration of the data collection period, analysis period, and as the manuscript is produced. Upon completion of the manuscript, the documents will be securely transferred to the WBAMC room 10015 and secured in a locked cabinet for a period of up two years. Upon completion of the three year, post-study period, the documents will be destroyed in accordance with WBAMC sensitive document disposal policies.

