All appropriate provider and nursing policies, safeguards and regulations governing the preparation and administration of parenteral medication within the WBAMC ED will be followed and standard of care for the injection of ketorolac will not be altered, omitted or deviated from industry, ethical, moral or hospital standards. The investigators will not have any part in preparation or administration of the ketorolac-this will be completely handled by WBAMC ED nursing staff and the order for the ketorolac will have already been approved and prescribed by the WBAMC attending ED provider through the EHR.

As the medication is prepared for administration, the investigator will educate the subject on the use of the VAS and annotate their pre-treatment pain score on the VAS form. For the purposes of this study, the VAS is a validated tool that will be used to objectively measure the subject's response to ketorolac.

The subject will then be injected intramuscularly with the dose of ketorolac randomized to the patient based on the Subject Study Number assigned to the randomized packet, which was assigned to that subject. Again, all appropriate provider and nursing policies, safeguards and regulations governing the preparation and administration of parenteral medication within the WBAMC ED will be followed and standard of care for the injection of ketorolac will not be altered, omitted or deviated from industry, ethical, moral or hospital standards.

Following the administration of ketorolac and at the 30 and 60 minute intervals, VAS scores will be recorded, the patient will be assessed for adverse effects (objective and subjective) and blood pressure and heart rate measurements will be taken. At the conclusion of the 60 minute period and documentation of the VAS and any adverse effects, the data collection phase will be considered complete. The subject will be notified that the study has concluded. The attending provider will then continue with evaluation, treatment, and disposition, as indicated.

As outlined during the consent process, additional analgesia will be available during the course of the study. The decision to provide additional analgesia will be made by the attending provider in consideration of the study subject's clinical scenario. Study subjects who receive additional analgesia will be unenrolled from the study at the time of administration of the additional analgesia.

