To measure the subject's reported level of pain on the VAS, the investigator will measure from the beginning of the scale to the vertical mark drawn by the subject. The "0 mark" on the metric tape measure will be aligned with the "0 mark" on the VAS form and the millimeters from the "0 mark" to the vertical line representing the subject's pain will be tallied. This distance will be annotated next to the scale for ease of reference. All VAS measurements will be completed and documented in the same manner for the 30 and 60 minute intervals. This study will use a previously validated measure of a 13 mm change in VAS to determine the minimum clinical significant difference (MCSD). (REF). Please refer to the statistical analysis portion of this document for more information about how this data will be used.

VAS measurements will not be taken during the data collection phase of this study. Only after data collection has been completed for the entire study and all VAS forms have been completed for all study subjects will the investigators actually measure and record the VAS scores. The purpose of not measuring the VAS at the time of data collection is to reduce research bias. Measurement of all VAS forms will take place at a predetermined time and place for both investigators (PI and AI). During the VAS measurement process, all investigators involved with the research must agree upon the measurement obtained. If, there is a discrepancy with the measurement process or measurement obtained, the VAS will not be used and the patient will be excluded from the study. The methodology for measuring the VAS will be based on prior literature explaining the process, in order to reduce inaccuracies 26.

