**Descriptive Statistics Data.**

Descriptive statistics data will be gathered to find correlation between subject demographics (age and gender) and location and duration of pain. These data will be obtained on the Ketorolac Research Form which is completed by the subject and will be included as descriptive statistics only. The data may or may not be analyzed for statistical significance, this will be at the discretion of the statistician. Furthermore, data pertaining to subjects requiring analgesia beyond the ketorolac used for this study, will also be collected for descriptive purposes only. Furthermore, data pertaining to subjects requiring analgesia beyond ketorolac, will be collected for descriptive purposes only. The data will be collected on the Ketorolac Data Collection Workbook, along with the other data.

At the completion of the entire data collection period for the entire study, VAS measurements will be obtained based on the methodology above and all data pertaining to the primary outcome (VAS scores), secondary outcome (adverse events) and descriptive statistics (from the Ketorolac Research Form) will be transcribed on to a Microsoft Excel work sheet. Any PHI or PII at this point will be de-identified and only the Subject Study Number will be used for identification. All paper documents will be secured in a manner previously described. The Excel worksheet is located on the PIs government issued common-access-card protected laptop. Access to this laptop requires both a common-access-card and a personal identification number (PIN) assigned to that specific common-access-card. The worksheet will therefore be highly secure and saved to the hard drive of the PIs laptop. The hard drive on the computer can only be accessed by the PI (as previously discussed) and network system administrators with permission. The AI for this research may also have a copy of the de-identified data, however, the data will be stored and secured in the exact same manner as the PI (common-access-card and PIN protected). All measures will be taken to protect the information of the study, however no PHI or PII will be stored on the Microsoft Excel work sheet.

**10.3 At any point in the study, will you request, use, or access health information in any form, including verbal, hard copy and electronic?**

Yes  No

**10.4 Review the definitions below and respond to the following two questions. If you are not sure of the answers, email [contact] for assistance.**

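### Section 10.14 has each subject's data entered in Excel every study day without exempting the VAS, which conflicts with the rule in 10.2 that no VAS is measured until all subjects have finished

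*Protocol*

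**What the plan says.** **Section 10.14 (Managing Data).** The paragraph first says that pain levels go on the three VAS forms and that descriptive data and adverse effects go on the Ketorolac Research Form. Its data-entry sentence then begins "At the end of each study day, the data from each" and continues "study subject will be transcribed on to the Excel document on the PIs government issued laptop". The PI keeps that laptop throughout the study.

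**Section 10.2, Primary Outcome Variable Data.** "VAS measurements will not be taken during the data collection phase of this study". Measurement comes "Only after data collection has been completed for the entire study and all VAS forms have been completed for all study subjects", in one session at which all investigators must agree on each reading. The reason is given: "The purpose of not measuring the VAS at the time of data collection is to reduce research bias".

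**Section 10.2, Descriptive Statistics Data.** "At the completion of the entire data collection period for the entire study, VAS measurements will be obtained", and at that same point the VAS scores together with the "secondary outcome (adverse events) and descriptive statistics (from the Ketorolac Research Form) will be transcribed on to a Microsoft Excel work sheet". Rows are identified only by Subject Study Number.

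**Section 10.1, Randomization and Study Subject Packet Creation.** The Subject Study Number contains 15 or 60 for the dose, and it is written on the packet and on every document inside.

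**SAP.** It names the tests. It does not say when the VAS is read or entered, or which reading is analysed.

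**The concern.** The protocol gives two incompatible times for moving data from paper to the spreadsheet, and one of them touches a safeguard that the investigators wrote deliberately. A VAS mark becomes a number only when someone measures it. Entering VAS values on the day of the visit would therefore require the measurement that 10.2 forbids until the end.

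What is at stake is the independence of the primary measurement from knowledge of dose and of emerging results. The investigators who consent subjects (section 13.4) also decide when a VAS form is unusable and must be redone, categorize subjective adverse events, and exclude a patient whose VAS reading they cannot agree on (section 10.2). A dataset in millimetres that builds up by dose could colour those judgements. A same-day reading could also anchor the later joint reading, and no rule says which of the two would count.

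**Working it through.** No figure is in dispute. The planned sample size (section 11.5: margin 13 mm, SD 27, true difference 0, one-sided alpha 0.05) reproduces: with the noncentral t distribution, power is 0.7998 at 54 per arm and 0.806 at 55, against 55 stated. Nothing here changes it. The check is a comparison of the text.

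| Question | Section 10.14 | Section 10.2 |
|---|---|---|
| When are VAS lines measured? | Not stated | After all subjects have finished |
| When are VAS values entered? | End of each study day, if the data include the VAS | After the whole collection period |
| When are adverse-event and descriptive data entered? | End of each study day | After the whole collection period |
| Is any data type exempted? | No | Not applicable; all three types are named together |

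1. **Broad reading of 10.14.** The sentence covers everything on the forms just listed, including the VAS. It then contradicts both parts of 10.2 and requires early measurement.
2. **Narrow reading of 10.14.** The sentence covers only what exists as data that day, which means adverse-event and descriptive data. The VAS safeguard survives, but 10.14 still contradicts Descriptive Statistics Data, which puts those items at the end too. Adverse events, the secondary outcome, would accumulate by dose during recruitment.
3. **The sections conflict on either reading.** Only the consequence differs.
4. **Can the arm be seen in the sheet?** Yes. Rows carry the Subject Study Number, which contains the dose. Section 10.1 adds that the randomization block number alone is enough to tell the group.
5. **Who could see it?** The PI holds the laptop. Descriptive Statistics Data lets the second investigator hold a copy, although section 14.3 says only the PI has access.
6. **Ceiling on reach.** 122 subjects × 3 VAS readings = 366 readings. This counts what could be touched; it does not estimate bias. The documents give nothing from which a shift in millimetres could be derived and set against the 13 mm margin.

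**The case against.** The strongest reply is that the specific rule governs the general one. Section 10.14 mentions no measuring and no millimetres, while 10.2 expressly prohibits early measurement, so no VAS number would exist to transcribe on the day. This is a fair reading and may well be what was intended. It leaves the adverse-event and descriptive conflict in place, and 10.14 does not state the exemption it depends on.

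Several stronger readings are tempting, but the documents do not support them:

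- **That 10.14 orders same-day measurement by one person.** It says neither; that is an inference from the missing exemption.
- **That deferred reading is the only protection of the primary measurement.** The protocol also has single-blinding (9.4), separate forms to limit response bias (10.1), an unmarked line checked to be 100 mm, and agreement of all investigators on each reading (10.2).
- **That Medication Administration (10.1) describes a bedside measurement.** There "the investigator will educate the subject on the use of the VAS and annotate their pre-treatment pain score on the VAS form". But 10.2 uses the same verb for the subject's own mark on the line, and the description of the VAS forms in 10.1 has the subject mark the pre-treatment form. The sentence is loose, and the point does not need it.
- **That a running tally could decide whether to keep enrolling.** No interim analysis or results-based stopping rule appears, and enrolment is fixed at 122.
- **That following 10.2 removes the exposure.** Investigators already know the dose, handle dose-coded forms and check each mark. Daily entry would turn rough impressions into a tabulated dataset; it does not create the exposure.

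**Conclusion.** The conflict is real and concerns handling of the primary outcome. Section 10.14 sets daily transcription without exempting the VAS, and 10.2 sets measurement and all transcription after the last subject. If 10.14 is applied to the VAS, the stated safeguard against investigator bias in measurement is lost, in a sheet that shows the dose. If it is applied only to the other data, the safeguard stands and a smaller inconsistency in timing remains.

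The harm is conditional on the broad reading being followed, and it comes on top of the exposure already present in a single-blind trial with dose-coded forms. Its size cannot be computed; the figure of 366 readings is a ceiling on reach only. The point deserves correction because the wording is easy to follow the wrong way and the remedy is nearly free. It is not evidence that early measurement or an interim look is planned.

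**What to change.** Reconcile section 10.14 with both parts of 10.2:

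1. State in 10.14 that no VAS value is measured for analysis, or entered, until the last subject has completed the 60-minute assessment.
2. State there and in the SAP that the joint end-of-study reading is the only VAS value analysed. Section 12.5 requires at least 20 mm for entry, so say how that check is made and that any reading taken for it is not analysed.
3. Give one time for entering adverse-event and descriptive data, and use it in both sections. Protecting the VAS does not require barring their entry until the end. Either time can be defended, and prompt entry helps to catch errors early.
4. Put an identifier that does not show the dose on the VAS forms and in the Excel sheet, and keep the code list from the readers until the joint reading is finished, so that it is masked to arm. Dropping the 15 or 60 alone is not enough, because the block number also reveals the group.

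The cost is a few sentences and a separate code list. VAS entry is left to the end, as 10.2 already plans. Sample size, treatment and visit procedures do not change. Bedside knowledge of the dose remains, as the single-blind design accepts.

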#### **10.15 Managing Data (Data Management and/or Sharing Plan) and/or Human Biological Specimens for Future Research:**

If the study involves collecting, storing, or banking human specimens, data, or documents (either by the Investigator or through an established repository) for FUTURE research, address. How the specimens /data will be used, where and how data/specimens will be stored (including shipping procedures, storage plan, etc.), whether and how consent will be obtained, procedures that will fulfill subjects' request as stated in the consent, whether subjects may withdraw their data/specimens from storage, whether and how subjects may be recontacted for future research and given the option to decline, whether there will be genetic testing on the specimens, who will have access to the data/specimens, and the linkage, the length of time that data/specimens will be stored and conditions under which data/specimens will be destroyed.

N/A

